4.7.3.1 Confirmatory analysis

The key secondary incidence variables (plasma glucose recovery within 30 minutes, within 20 minutes, within 15 minutes, within 10 minutes, in hierarchical order for inference) will be analyzed using descriptive statistics (frequency and percentage) by treatment group. Inferential treatment group comparisons will be assessed via pairwise tests of independent binomial proportions (dasiglucagon versus placebo, GlucaGen versus placebo) using Fisher's exact test for each pairwise comparison.

CONFIDENTIAL

Sponsor:	Zealand Pharma A/S	Protocol Number:	ZP4207-16137
----------	--------------------	------------------	--------------

The key secondary endpoints of plasma glucose changes from baseline within 30 minutes, within 20 minutes, within 15 minutes, and within 10 minutes after study drug injection or at the time of rescue, will be analyzed with the plasma glucose changes from baseline at rescue carried forward in those subjects who require rescue IV glucose before plasma glucose ≥ 20 mg/dL recovery. Each of these changes from baseline variables will be analyzed using an Analysis of Covariance model, with treatment group modelled as a fixed effect and with the baseline plasma glucose modelled as a covariate. The dasiglucagon versus placebo treatment group difference will be evaluated inferentially as a least squares means contrast, using a two sided t-test at the 0.05 significance level, first for the 30 minute changes from baseline, and then sequentially for the 20 minute, 15 minute, and 10 minute variables, until the first failure to reject.

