4.7.4 Secondary clinical efficacy (PD) endpoints

- Time to first plasma glucose concentration of ≥ 70 mg/dL (3.9 mmol/L) without administration of rescue IV glucose.
- Plasma glucose response as area under the curve above baseline from time zero to 30 minutes, $AUC_{0-30min}$.

Secondary clinical efficacy endpoints will be assessed based on plasma concentration data from samples collected at the dosing visit (Visit 2).

Unless otherwise stated, the population base of analysis will be the Full analysis set.

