4.7.4.1 Analysis of secondary clinical efficacy (PD) endpoints

1. Time to first plasma glucose concentration ≥ 70 mg/dL from baseline. This time to-event endpoint will be evaluated using a Kaplan-Meier approach, with treatment group as a stratification factor, analogous to that used for the primary endpoint analysis. Differences between the KM curves (dasiglucagon versus placebo, GlucaGen versus placebo) will be evaluated inferentially using pairwise two-sided log rank tests. If the ≥ 70 mg/dL endpoint is not met within 45 minutes post-dosing, the time of the last valid plasma glucose measurement up to 45 minutes will be the censoring time.
2. The AUC will be calculated as the baseline-adjusted area under the plasma glucose profile over time:
 - a. $AUC_{0-30min}$: restricting the time window to the 0 to 30 minutes interval.

The log-transformed AUC endpoint will be analyzed using an analysis of covariance (ANCOVA) model with treatment as fixed effect and baseline plasma glucose modelled as a covariate. The least squares means treatment group differences will be back transformed (anti logged) for presentation as a ratio of the treatment group geometric means, with their corresponding 95% CI.

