4.12 Subject Withdrawals and Missing Data

Failure is defined for the primary time-to-recovery endpoint as censored with time to recovery set to the maximum follow-up time, here 45 minutes. Individuals will be set to 'failure' in case of receiving rescue IV glucose, discontinuation due to treatment or discontinuation in connection with the induced hypoglycemia state. Only if an intermediate assessment is missing independent of rescue treatment, study treatment or an adverse event including hypoglycemia, a linear interpolation can be applied to impute a missing value.

The same construct of imputation for missing values applies for the analysis of the plasma glucose AUC0-30min.

In the case of subject withdrawal, no imputation of values for PK or PD measurements will be done. Analyses will be done on valid cases only, i.e., no imputation techniques such as last observation carried forward will be applied.

CONFIDENTIAL

Sponsor:	Zealand Pharma A/S	Protocol Number:	ZP4207-16137
----------	--------------------	------------------	--------------

Methods for Handling Missing Dates

All analyses and descriptive summaries will be based on the observed data. For the subject data listings, no imputation of incomplete dates will be applied. The listings will present the incomplete dates without any change.

Missing or Partial Death Dates

- If the entire date is missing, the death date will be imputed as the day after the date of last contact.
- If the day or both day and month is missing, the death date will be imputed to the maximum of the full (non-imputed) day after the date of last contact and the following:
 - If day is missing, day will be 1st of the month
 - If both day and month are missing, death month and day will be January 1st.

Missing Dates in Adverse Events/Concomitant Therapies

Dates missing the day or both the day and month of the year will adhere to the following conventions:

- The missing day of onset of an AE or start date of a therapy will be set to:
 - first day of the month that the event occurred, if the onset yyyy-mm is after the yyyy-mm of first study treatment
 - the day of the first study treatment, if the onset yyyy-mm is the same as yyyy-mm of the first study treatment
 - the date of informed consent, if the onset yyyy-mm is before the yyyy-mm of the first treatment
- The missing day of resolution of an AE or end date of a therapy will be set to:

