5.2 Conventions

Unless otherwise specified, in summary tables of continuous variables, the minimum and maximum values will be displayed to the same number of decimal places as the raw data, the mean and median will be presented to one extra decimal place compared to the raw data, and the standard deviation will be displayed to two extra decimal places compared to the raw data. PK and PD data will be reported with 3 significant digits. Wherever possible data will be decimal aligned.

Unless otherwise specified frequency tabulations will be presented by number and percentage, where the percentage is presented in brackets to 1 decimal place.

P-values, if applicable, will be presented to 3 decimal places. If a p-value is less than 0.05 but is greater than or equal to 0.01, then an asterisk (*) will be added next to this value. If a p-value is less than 0.01 but is greater than or equal to 0.001, then two asterisks (**) will be added next to this value. Finally, if the p-value is less than 0.001 then three asterisks (***) will be added next to this value and it will be presented as <0.001. If the rounded result is a value of 1.000, it will be displayed as >0.999. Any date information in the listing will use the *date9.* format, for example, 06OCT2017. In the listing, a unit associated with a variable will be presented only once within parentheses either below or next to that variable in the heading portion. If a parameter has multiple units, each unit will be displayed only once, as applicable.

All tables will have their source listing referenced in a footnote. Listings should be sorted by treatment group, subject and visit and have the source data received by data management referenced in a footnote. All tables and listings will be converted into Microsoft Word documents and collated into two complete documents.

The following conventions apply for calculation of PK parameters:

- Any BLQ (<LLOQ) values that occur before the first quantifiable concentration will be replaced with zero.
- If a BLQ (<LLOQ) value occurs after a quantifiable concentration in a profile and is followed by a value of LLOQ or above, then the BLQ (<LLOQ) will be replaced with LLOQ/2.
- If two BLQ (<LLOQ) values occur in succession, the profile will be deemed to have terminated at the final quantifiable concentration and subsequent LLOQ or above values will be treated as 'missing'.

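### The plan log-transforms a baseline-adjusted glucose AUC that can be zero or negative and gives no rule for such values, so the ratio versus placebo does not describe the Full analysis set

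*SAP*

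**What the plan says.** Section 4.7.4 defines the endpoint: "Plasma glucose response as area under the curve above baseline from time zero to 30 minutes". It makes the Full analysis set the default population. Section 4.7.4.1 gives the derivation: "The AUC will be calculated as the baseline-adjusted area under the plasma glucose profile over time". It then gives the model: "The log-transformed AUC endpoint will be analyzed using an analysis of covariance (ANCOVA) model with treatment as fixed effect", with baseline glucose as covariate, and back-transforms the result "for presentation as a ratio of the treatment group geometric means, with their corresponding 95% CI".

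Three other places bear on it.

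- Section 4.12 on missing data: "The same construct of imputation for missing values applies for the analysis of the plasma glucose AUC0-30min". The construct it points to sets rescued or discontinued subjects to failure in the time-to-event analysis and allows interpolation of an unrelated missing intermediate sample. For withdrawn subjects it adds: "Analyses will be done on valid cases only, i.e., no imputation techniques such as last observation carried forward will be applied".
- Section 5.2 has replacement rules for values below the quantification limit, introduced by "The following conventions apply for calculation of PK parameters".
- Section 4.7.3.1 keeps the glucose changes from baseline on their original scale: "The dasiglucagon versus placebo treatment group difference will be evaluated inferentially as a least squares means contrast". It carries the change at rescue forward in subjects rescued before recovery.

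**The concern.** A subject in insulin-induced hypoglycemia who receives placebo may show a flat or falling glucose. The baseline-adjusted area is then at or below zero and has no logarithm. SAS returns a missing value and PROC GLM omits the record. The SAP does not state this exclusion, but it prescribes nothing else. The subjects removed are the poorest responders, so the analysis would no longer cover the population that section 4.7.4 names. If the programmer instead substitutes a small positive number, the ratio depends on which number is chosen.

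A second gap adds to this. The SAP does not say whether glucose measured after rescue IV glucose enters the AUC. If it does, treatment failures are credited with area produced by the rescue.

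**Working it through.** **1. Is there a rule for values at or below zero?** Section 4.12 deals with missing samples, and an observed area of zero or less is not a missing sample. Its failure category belongs to a time-to-event analysis and assigns no AUC. Section 5.2 is limited to PK parameters. The trapezoidal code in section 4.15 has no baseline subtraction and no floor, so it does not settle whether the area is net or truncated. No rule exists.

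**2. What the planning figures imply.** The SAP states no figure for the AUC. Its nearest quantitative statement is section 3.9: 78 and 39 subjects, exponential medians of 10 and 20 minutes, 45 minutes of follow-up, 90% power.

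- Events by 45 minutes: 1 − 2^(−4.5) = 0.956 and 1 − 2^(−2.25) = 0.790, so 78 × 0.956 + 39 × 0.790 = 105.4 events.
- With hazard ratio 2 and two-thirds allocation, Schoenfeld's formula gives 91.8%. A simulated log-rank test (3,000 runs) gives 90.4%. The stated 90% reproduces.
- No 20 mg/dL rise by 30 minutes: placebo 2^(−30/20) = 35%, about 14 of 39; dasiglucagon 2^(−30/10) = 12.5%, about 10 of 78.

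Areas at or below zero would come mainly from this group, which is proportionally larger on placebo. It is not a count of them, because a rise of under 20 mg/dL can still give a positive area.

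**3. Possible loss, net-area reading.** The mean and SD are assumptions. With a normally distributed time-averaged change from baseline, P(AUC ≤ 0) = Φ(−mean/SD). Expected number of 39 in brackets:

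| Assumed placebo mean (mg/dL) | SD 5 | SD 8 | SD 12 |
|---|---|---|---|
| 0 | 50% (19.5) | 50% (19.5) | 50% (19.5) |
| 3 | 27% (10.7) | 35% (13.8) | 40% (15.7) |
| 5 | 16% (6.2) | 27% (10.4) | 34% (13.2) |
| 10 | 2% (0.9) | 11% (4.1) | 20% (7.9) |

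**4. How far the ratio depends on the unwritten rule.** Assumed AUCs in mg/dL·min: dasiglucagon mean 1000, SD 350; placebo SD 200; normal; 400,000 draws per row. Both ratios are geometric.

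| Placebo mean | Placebo share ≤ 0 | Ratio if dropped | Ratio if floored at 1 |
|---|---|---|---|
| 0 | 50% | 8.8 | 88.4 |
| 100 | 31% | 6.6 | 29.7 |
| 200 | 16% | 4.8 | 10.9 |
| 300 | 7% | 3.5 | 5.0 |

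In the second row, dropping raises the retained placebo mean from 100 to 202, so the arithmetic difference falls from about 900 to about 800. The floor of 1 is itself arbitrary, so the last column is not a correct value. It shows only how much the answer moves.

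**The case against.** Several points on the other side stand.

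- **Standing of the endpoint.** Section 2.2 lists this AUC under other secondary endpoints, and it lies outside the hierarchy in section 4.7.1. Glucose change is tested confirmatorily on the untransformed scale. A reader might infer that the confirmatory claim or the type I error is at risk; the SAP does not support that.
- **Direction.** Dropping poor placebo responders raises the placebo mean, and counting post-rescue glucose does the same. Both work against dasiglucagon. This is likely rather than certain, since small positive areas that stay in pull the placebo geometric mean down.
- **Size.** A reader might take 14 of 39 as the expected loss. It is not a document-based figure. At the planning median, 65% of placebo subjects rise by at least 20 mg/dL within 30 minutes, and a linear rise to 20 at 30 minutes averages 10. An assumed mean of 13 with SD 8 gives Φ(−1.625) = 5%, or 2 of 39. The SAP expects a placebo median beyond 20 minutes, so the loss could be larger.
- **Truncated reading.** If area below baseline counts as zero, the AUC is zero only when none of the ten scheduled post-dose samples to 30 minutes exceeds baseline. That is probably rarer than a net area at or below zero.
- **Competing mechanisms.** If post-rescue glucose is included, some rescued subjects have a positive area and are not dropped. The two effects cannot both apply in full.
- **Which contrast.** The secondary objective compares dasiglucagon with GlucaGen. Between two active arms most areas should be positive, and a log-scale ratio is reasonable. It would be too strong to call every ratio from this model unusable, or to say that the loss falls almost wholly on placebo; the latter depends on an assumed dasiglucagon distribution.

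None of this supplies the missing rule.

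**Conclusion.** The analysis is wrong as written and should be corrected, but it does not threaten the trial's main conclusions. A quantity that can be zero or negative is logged without a rule for such values. The default is exclusion by outcome, expected to be proportionally heavier on placebo, so the ratio versus placebo and its interval estimate no defined Full analysis set quantity. The likely direction is to understate the dasiglucagon effect.

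The number lost is unknown. The range of about 2% to 50% of placebo subjects rests on a net area, normality, and assumed time-averaged means of 0 to 10 mg/dL with SDs of 5 to 12 mg/dL. The finding itself rests only on the text: no rule for non-positive areas, no choice between net and truncated area, and no statement on glucose after rescue.

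**What to change.** Before unblinding, amend section 4.7.4.1 as follows.

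1. State whether area below baseline counts as negative or as zero.
2. Analyse AUC0-30min untransformed with the same ANCOVA (treatment, baseline glucose). Report the LS-mean difference with 95% CI for all Full analysis set subjects. This is the model section 4.7.3.1 already uses for glucose changes.
3. For the AUC calculation, carry the change from baseline at rescue forward to 30 minutes in subjects rescued before recovery, in line with section 4.7.3.1. Cross-refer to section 4.12 so that its bar on carrying observations forward, written for withdrawals, is not read as a conflict.
4. Keep the log scale for PK AUC and Cmax, which are not baseline-subtracted. A log-scale ratio of dasiglucagon to GlucaGen may stay as supportive.

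The cost is a few sentences and minor programming. The downside is that the effect versus placebo appears as a difference instead of a ratio.

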4.7.5 Exposure (PK) endpoints

- Plasma dasiglucagon and GlucaGen concentrations from time zero to 90 minutes:
 $AUC_{0-90min}$, C_{max} , and t_{max} .

CONFIDENTIAL

Sponsor:	Zealand Pharma A/S	Protocol Number:	ZP4207-16137
----------	--------------------	------------------	--------------

4.7.5.1 Analysis of exposure (PK) endpoints

AUC will be derived as the area under the individual plasma dasiglucagon/GlucaGen concentration profile for PK from 0 to 90 minutes or last valid measurement if this measurement is assessed sufficiently close to 90 minutes (decision to be taken at the blinded data review meeting). The standard trapezoidal method will be used, based on actual rather than nominal timepoints.

Cmax will be determined as the maximum of all valid plasma dasiglucagon/GlucaGen concentrations.

Tmax will be determined as the timepoint where the maximum of all valid plasma dasiglucagon/GlucaGen concentration measurements for each measurement series is observed.

The log-transformed PK endpoints AUC and Cmax will be analyzed in the same way as the AUC endpoints.

As tmax is a highly discrete endpoint, Wilcoxon's rank sum test for unpaired observations will be used to assess differences between the two treatment groups.

Exposure endpoints will be summarised for the Full analysis set, which is identical to the Safety analysis set.

CONFIDENTIAL

Sponsor:	Zealand Pharma A/S	Protocol Number:	ZP4207-16137
----------	--------------------	------------------	--------------

Table 4-2: Overview of Efficacy Analyses

Efficacy Endpoint	Statistical Analyses	SAS Procedure
Endpoints with binary response outcomes:		

 Plasma glucose recovery within 30 minutes, within 20 minutes, within 15 minutes, and within 10 minutes after study drug injection without administration of rescue IV glucose. 	
 Fisher's exact test for each pairwise comparison 	
 FREQ LOGISTIC
Endpoints with continuous outcomes:		

 Plasma glucose changes from baseline changes from baseline within 30 minutes, within 20 minutes, within 15 minutes, and within 10 minutes after study drug injection or at the time of rescue. 	
 Changes from baseline: Analysis of Covariance model, with treatment group modeled as a fixed effect and with the baseline plasma glucose modeled as a covariate Changes from baseline: Two sided t-test at the 0.05 significance level 	
 GLM
Endpoints with time-to-event outcomes:		

 Time to plasma glucose recovery Time to plasma glucose recovery without censoring at the time of recovery for those subjects who require rescue IV glucose before 45 minutes Time to plasma glucose recovery with censoring at the time of administration of rescue IV glucose before 45 minutes 	
 Kaplan-Meier (KM) estimates stratified by treatment group and injection site Pairwise two-sided log rank test Cox proportional hazards (CPH) time to event statistical model with treatment group and injection site modeled as categorical effects, and baseline plasma glucose modeled as a continuous covariate Kaplan-Meier plots, both stratified by injection site and without stratifying by injection site 	
 LIFETEST PHREG or TPHREG

4.8 Exploratory Analysis

Exploratory analyses will include descriptive statistics and modeling analogous to that done for key secondary endpoints. However, treatment group comparisons will be summarized without inference intent.

CONFIDENTIAL

Sponsor:	Zealand Pharma A/S	Protocol Number:	ZP4207-16137
----------	--------------------	------------------	--------------

- Plasma glucose concentration ≥ 70 mg/dL (3.9 mmol/L) or increase of ≥ 20 mg/dL (1.1 mmol/L) within 30 minutes after study drug injection without administration of rescue IV glucose.
- Plasma insulin response as area under the curve above baseline from time zero to 60 minutes, $AUC_{0-60\text{ min}}$.

Plasma insulin concentrations measured pre-dose and at 30 and 60 minutes after dosing (see Protocol Table 3 “Schedule of Procedures”) will be presented individually. A summary table per timepoint will be provided. The $AUC_{0-60\text{min}}$ will be determined and a summary presented.

4.9 Safety Analysis

4.9.1 Adverse events

Adverse events and serious adverse events will be summarised separately by treatment by presenting the number and percentage of subjects having any event, having a related event, having an event leading to withdrawal, having an event in each MedDRA system organ class and preferred term, having each individual event and the severity, relationship and outcome of each event. Number of events is also presented. Missing severity, relationship or outcome will be classed as unknown.

A subject with more than one occurrence of the same adverse event in a particular system organ class will be counted only once in the total of those experiencing adverse event in that particular system organ class. If a subject experiences the same adverse event at more than one severity, or with more than one relationship to investigational product, the most severe rating or the stronger causal relationship to investigational product will be given precedence. Any missing severity, causality, or outcome will not be imputed and classed as unknown.

Summaries classifying both events according to severity and relationship will be presented.

AEs will be coded according to MedDRA, version 19.1. AE summary tables will include the number and percentage of subjects who experienced AEs summarized by system organ class and preferred term.

Only treatment-emergent adverse events (TEAEs) will be reported. TEAEs are undesirable events not present prior to medical treatment, or an already present event that worsens in intensity following the treatment.

Related events are defined as events that are probably or possibly related to study medication or with an unknown relationship.

Adverse event of special interest (AESI) is an event which, in the evaluation of safety, has a special focus (e.g. required by health authorities). In this trial hemodynamic changes, as defined below, are considered AESIs:

- Post-dose clinical signs, or measured vital signs, indicating a clinically significant drop in blood pressure including signs of orthostatic hypotension, vasovagal responses or bradycardia.

CONFIDENTIAL

Sponsor:	Zealand Pharma A/S	Protocol Number:	ZP4207-16137
----------	--------------------	------------------	--------------

- Post-dose change in pulse or blood pressure considered an event of hypo- or hypertension as judged by the investigator.

4.9.1.1 Subsets

An overall summary table will be provided showing the number and percentage of subjects with any:

- TEAE
- Severe TEAE
- Serious TEAE
- Drug-related TEAE
- Drug-related severe TEAE
- Drug-related serious TEAE
- TEAE leading to withdrawal
- TEAE with outcome death
- AESI

All other information collected (e.g., action taken) will be listed as appropriate.

Only treatment-emergent adverse events (commencing during or after exposure to study treatment) will be included in the adverse and serious adverse event summaries. Non-treatment-emergent events (starting prior to exposure to study treatment) will be included in the subject listings and flagged but not included in the above summaries. Where an AE start date is partially or fully missing, and it is unclear as to whether the AE is treatment emergent, it will be assumed that it is.

